protocols and tracking systems that have facilitated a detailed examination of the efficiency of recruitment efforts^{18,105,106,146}. We have also specifically examined issues related to dyadic vs. individual participation in research on partnered MSM¹⁸.

SAFETY MONITORING PLAN

Adverse Events Reporting

The Site PI is responsible for the detection and documentation of events meeting the criteria and definition of an AE or SAE. Study staff may ask PI questions concerning adverse events, but must formally report them via email. Information on unexpected events including serious adverse effects (SAEs) will be reported as per the policy of the IRB.

Information to be collected includes the nature, date of onset, stop date, intensity, duration, treatment, causality, and outcome of the event. Pls should follow usual clinical practices for reporting serious, unexpected events related to standard of care. SAEs that occur after 30 days after completion of the study will be collected only if they are considered by the PI to be related to study participation. In addition, any AE resulting in potential participant withdrawal must been reported to the PI prior to participant withdrawal when possible.

PIs must report any Adverse Event to the IRB within five business days of learning of it.

ETHICAL CONSIDERATIONS

Informed Consent Process

Site PIs must ensure that participants are fully informed about the purpose, responsibilities of participating and potential risks or other critical issues related to participation in the study. Written informed consent is obtained from every participant or, in those situations where consent cannot be given by participants, their legally acceptable representative, prior to clinical study participation.

The rights, safety, and well-being of study participants are the most important considerations and should prevail over interests of science and society. If there is any question that the prospective participant will not reliably comply with study procedures and/or follow-up, they should not be enrolled in the study.

REFERENCES

- CDC. Preexposure prophylaxis for the prevention of HIV infectionin the United States 2014. A clinical practice guideline. 2014. http://www.cdc.gov/hiv/pdf/prepguidelines2014.pdf. Accessed 4/25/2016.
- 2. Prevention CfDCa. HIV Surveillance Report. In: Prevention CfDCa, ed. Vol 272015.
- 3. CDC. HIV and substance use in the United States. 2013.

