Participants are considered enrolled in the study when they have completed informed consent. Randomization occurs immediately after the baseline appointment.

Informed Consent Process

Details of the study are reviewed with the prospective study participant by a research assistant who is trained and cleared to conduct assessments and is knowledgeable about the research study. This discussion is a critical component of the consent process and the prospective study participant will be given adequate time for this discussion and to read the written consent form. The research assistant is available to answer questions about the study including participant responsibilities, benefits, risks, and alternatives. The participant reviews the consent form and it is signed and dated by both the participant and study staff member conducting the assessment. A copy of the signed consent form will be given to the participant and the original will be kept securely by the project coordinator separate from other assessment materials.

Post-COVID: Participants review written consent information prior to their baseline appointment. The baseline survey link directs participants to a landing page containing detailed consent information. At the beginning of the baseline assessment, study staff provides an oral review of consent information and confirms age eligibility via Zoom. After reviewing this information, participants are asked to affirm their consent/assent to participate. A copy of the electronic consent form is emailed to the participant upon request.

Randomization Process/Systems

Participants are randomized at the end of their baseline assessment into one of two intervention conditions: 1) delivery of the 4 session PARTNER intervention or 2)

delivery of 4 education sessions. Each participant's condition is tracked in the access tracking database maintained by the project manager.

The study employs a stratified block randomization procedure with equate study conditions based upon 1) age discrepancy between partners, 2) relationship length, and 3) race and ethnicity using Qualtrics.

Schedule of Assessments

Sessions occurs approximately once per week for three weeks beginning one week after completion of the baseline assessment and session 1. There is a 12 week window for intervention completion, i.e. all four sessions must be completed within 12 weeks of the baseline assessment.

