Participants complete the first follow-up assessment 3 months after the baseline, and subsequent follow ups at 6, and 9 months after baseline with a final appointment scheduled for 12 months following the baseline appointment. Study staff should aim to schedule and complete these follow-ups as close as possible to each target date. To keep track of longitudinal data collection dates, assessment visit windows will be defined as 15 days prior and after the target as "in window." The assessment visit window for the 12 month follow-up ends 30 days after the target date. Site study staff should prioritize the completion of sessions before the first follow-up assessment, and should not schedule this follow-up less than 12 weeks after baseline if a participant is available to complete any additional sessions first.

Post-COVID: The 12-month assessment window ends 60 days after the target date.

Component	Baseline	Session 1	Session 2	Session 3	Session 4	3-Month Follow-Up	6-Month Follow-Up	9-Month Follow-Up	12-Month Follow-Up
Informed Consent	Х								Х
Randomization	Х								
CASI	Х					Х	Х	Х	Х
TLFB	Х					Х	Х	Х	Х
HIV Testing (Rapid for those not on PrEP –	Х						Х		Х

Architect for those on PrEP)								
STI Testing	Х					Х		Х
Fingernail Assay for Drugs	Х				Х	Х	х	Х
Dried Blood Spot (For those on PrEP)	х				Х	Х	Х	Х
PrEP Video			X					
Video Recall Survey for those who seen the Video				Х	х			х
Session feedback				Х				
Qualitative Interview								х

Managing and Tracking Study Visits

There are two different types of visits during the study timeline:

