Session Visits: Session visits refer to both the four education and four intervention sessions. Intervention sessions are conducted by trained and cleared MI-trained clinicians. Intervention sessions will be managed by the clinicians with their individual study participants. Clinicians will notify site study staff of whether visits were completed for tracking purposes, provide receipts for session compensation to site study staff, and upload audio files to Project Partners respective folder on the M drive as per study procedures. Education sessions are conducted by trained and cleared health educators. Education sessions will be managed by the educators with their individual study participants. Educators will notify site study staff of whether visits were completed for tracking purposes, provide receipts for session compensation to site study staff, and upload audio files to Project Partners respective folder on the M drive as per study procedures.

Research Visits: Research visits include all assessments including the baseline visit, the post-test assessment, and all other follow-up assessments. All participants, in either condition, are expected to complete five assessment visits as part of full participation in the study.

Study staff will schedule participants during times that they will be available or will contact other staff to ensure coverage for appointments. Study staff will also ensure that there is available space to conduct these assessments.

Future visits should be scheduled during the study visit. Study staff are expected to keep in touch with participants and remind them of the upcoming visit or reschedule if

needed. A reminder call should be made the day before a participant is due to come in for their visit (or the Friday before a Monday visit).

Retention and Follow Up

Session visits: For participants who are actively taking part in the PARTNER intervention or the Education control condition, site study staff will not add an additional level of outreach to the procedures.

Specimen Collection Pre-COVID

HIV testing will be performed at the baseline using the HIV 4th Generation assays and those will be administered following the below criteria:

- 1- Participants on PrEP, upon PrEP self-report confirmation will provide 1 tube of blood to send to the LAB for HIV Confirmatory testing with Architect equipment to avoid any inaccurate test results as a result of PrEP drugs in blood. Results are downloaded from the LAB's web portal.

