Drug use. During TLFB interviews, participants indicated whether they used any of 10 different drug types. Responses produced two count variables indicating the number of days participants used cannabis and the number of days they reported the use of any illicit drugs, including: cocaine, crack, methamphetamine, ecstasy, ketamine, GHB, and psychedelics. Self-reported drug use was corroborated by fingernail assay. See supplemental material for details.

Current PrEP uptake was assessed using a single survey item, "Have you ever been prescribed PrEP (HIV pre-exposure prophylaxis)?" Participants taking PrEP reported days they missed their PrEP on the TLFB interview. Responses were used to create a dichotomous variable indicating whether or not participants took PrEP on at least 57% of days (corresponding to at least 4 days out of 7 on average). Self-reported PrEP adherence was corroborated with DBS results. See supplemental material for details.

Sexual HIV TRB. During TLFB interviews, participants indicated days they had (insertive or receptive) anal sex with any casual partners and whether a condom was used. Responses were aggregated to create a variable indicating the number of times the participant had CAS with a casual partner. If participants were prescribed PrEP and reported missing 13 doses or fewer, they were assigned a value of 0, reflecting that the use of PrEP on at least 4 of 7 days is sufficient to achieve reductions in HIV TRB (28). Self-reported CAS with casual partners was corroborated by bacterial STI diagnosis. See supplemental material for details.

Putative moderators

Relationship satisfaction was assessed using the approximation to ideal subscale of Kurdek's (29, 30) Multiple Determinants of Relationship Commitment Inventory (MDRCI). The subscale consists of 4 items (e.g., "My current relationship comes close to matching what I would consider to be my ideal relationship"). Response options ranged from 1 (strongly disagree) to 5 (strongly agree). Total score reliability was good (Cronbach's $\alpha = .848$).

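### No masking of outcome interviewers is stated, and the session-tracking steps reveal the arm to the staff category that conducts the interviews

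*Combined protocol and SAP*

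**What the plan says.** - **Randomization Process/Systems:** "Participants are randomized at the end of their baseline assessment into one of two intervention conditions". Each participant's condition is held in a tracking database kept by the project manager. No limit on access is described.
- **Managing and Tracking Study Visits:** MI clinicians deliver PARTNER and health educators deliver the control. For the first group, "Clinicians will notify site study staff of whether visits were completed for tracking purposes"; for the second, "Educators will notify site study staff of whether visits were completed for tracking purposes". Both also hand session receipts to site study staff. For research visits, "Study staff will schedule participants during times that they will be available or will contact other staff to ensure coverage for appointments".
- **Schedule of Assessments:** study staff are told to schedule and complete the follow-ups near their target dates. In the same paragraph, "Site study staff should prioritize the completion of sessions before the first follow-up assessment". The table lists a "Video Recall Survey for those who seen the Video". The video belongs to PARTNER Session 3. As best the damaged table can be read, the survey falls at follow-up at 3 and 12 months.
- **Informed Consent Process:** the research assistant cleared to run assessments appears at signature as the "study staff member conducting the assessment".
- **Primary outcomes:** "During TLFB interviews, participants indicated whether they used any of 10 different drug types". Casual-partner CAS and missed PrEP doses also come from the TLFB. PrEP uptake is a single survey item.
- **Quantitative Analysis Plan:** fingernail assays, DBS and bacterial STI diagnoses are compared with self-report. Intervention effects on the two growth slopes are judged with one-sided p-values.

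The documents do not mention masking of assessors.

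**The concern.** Participants in a trial of motivational interviewing against education cannot be masked, so the interviewer is the point in outcome collection where masking could be applied. A TLFB interview relies on prompting and probing. An interviewer who knows the arm may probe differently without intending to. Three outcomes are exposed: drug-use days, CAS with casual partners, and PrEP adherence.

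Missed doses count twice. They define adherence, and a prescribed participant who reports 13 or fewer missed doses is assigned zero sexual risk. One shift in dose reporting can therefore move two primary outcomes. Because the tests are one-sided, a shift in the hypothesised direction goes straight into the rejection region.

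**Working it through.** **1. Does the arm reach the interviewers?**
- Notices and receipts come from clinicians (PARTNER only) or educators (control only), so the sender reveals the arm.
- The recipients are site study staff. They need session status, because they must favour session completion when booking the 3-month visit.
- Study staff schedule and complete the follow-ups, and the assessor is called a study staff member.
- No step separates the notified staff from the interviewers. Disclosure to the category is explicit; disclosure to the individual interviewer is a strong inference from shared wording.
- The baseline TLFB precedes randomisation, so only follow-up interviews are exposed.

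**2. Do the biomarkers close the gap?**
- Agreement is reported pooled, never by arm, and the outcome models use the self-reported variables.
- The nail assay covers about 6 months (Specimen Collection Pre-COVID), while the drug count covers 30 days (Power analyses). At the 3-month visit the nail window starts at 3 − 6 = −3 months, before randomisation.
- The nail comparison is positive/negative against any use, so it cannot check a number of days. It names cannabis, cocaine, crack and amphetamine; the outcome also counts ketamine, GHB, ecstasy and psychedelics.
- Agreement for illicit drugs is stated only as at least 55% of nail-positive participants.
- STI tests are at baseline, 6 and 12 months, and the STI variable also accepts self-reported diagnoses.

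**3. The plan's own yardstick.** Inputs: 240 participants, equal allocation (120 per arm); power .80; alpha .05; education rates 3 to 9; dispersion k from 1 to 4; exposure 30. With m = rate × exposure,

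`Var(ln RR) = (1/n)(1/m + 1/(m·RR)) + 2k/n`, solved for `−ln RR = (1.96 + 0.842)·SE`.

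- Rate 9, k = 1 (m = 270): SE ≈ 0.129, RR = 0.696; the plan states 0.70.
- Rate 3, k = 4 (m = 90): SE ≈ 0.259, RR = 0.484; the plan states 0.48.

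Both reproduce. One-sided alpha with 96 per arm (80% retained) also fits, at 0.698 and 0.487. No figure in the plan is disputed here.

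**4. Illustration of a reporting difference.** Assume no true effect, 120 per arm, one time point and one-sided .05. PARTNER participants report a fraction q of the control use days purely through reporting. The values of q are assumptions, since the documents give no arm-specific reporting rates. The mean μ is use days over the 30-day window.

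`SE = sqrt(2(1/μ + k)/120)`; `P(reject) = 1 − Φ(1.645 − |ln q|/SE)`

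| | SE | q = 0.90 (abs. ln q = 0.105) | q = 0.85 (abs. ln q = 0.163) |
|---|---|---|---|
| μ = 9, k = 1 | 0.136 | 19% | 33% |
| μ = 3, k = 4 | 0.269 | 10.5% | 15% |

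Using the variance formula of step 3 with the same means changes 33% to 32% and leaves the other entries the same to rounding. With 96 per arm, q = 0.90 gives 10% to 17%. The nominal rate is 5%.

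**The case against.** The strongest reply has five parts.

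- **Safeguards exist.** A reader might infer that the plan does nothing to limit reporting bias. That is not supported: each TLFB outcome has a biological comparison and the control is attention-matched. This stands. What remains is that the comparisons are not made by arm and do not enter the primary models.
- **The link is not stated.** A reader might infer that interviewers definitely know the arm. The documents also name research assistants, a project manager and a project coordinator, and never say that the person notified conducts the TLFB. Nor do they say who runs the Qualtrics randomisation or who gives the video survey. This stands, so the claim is that interviewers may know.
- **Not every primary outcome is reached.** PrEP uptake is a survey item and lies outside the interviewer route. This stands.
- **The illustration is not the plan's test.** The plan fits piecewise growth models and examines the slopes only after a significant overall likelihood test. A constant follow-up difference would load mainly on Slope 1, not Slope 2. The assumed differences also mix participant and interviewer reporting. All of this stands.
- **Timing.** The version is dated January 2024, reports follow-up comparisons through 12 months and describes analyses in the past tense. Procedural changes may be too late for data already collected. This stands and shapes the fix.

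None of these points supplies a masking step or a comparison of agreement by arm.

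**Conclusion.** The concern holds in limited form. As written, the plan discloses the arm to the staff category that conducts follow-up assessments and states no interviewer masking. Drug-use days, casual-partner CAS and PrEP adherence are therefore open to interviewer-related bias, and the existing biomarker checks, pooled and outside the models, would not show whether it differed by arm.

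The direction and size of any actual bias cannot be determined from the documents. A reader might take 10% to 33% as the trial's false-positive rate. It is not: it assumes a 10% or 15% reporting difference, one time point and a simple rate-ratio test without the overall gate. Nor is it the amount that masking would prevent, since masking interviewers removes only their share of the bias. The matter should be addressed, but it does not by itself invalidate the outcomes.

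**What to change.** **For any remaining visits:**
- Restrict the arm and provider fields in the tracking database to the project manager.
- Route session notices and receipts to staff who do not conduct TLFB interviews.
- Complete the TLFB before the video recall survey and the qualitative interview.
- Record at each follow-up whether the interviewer knew the arm.

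**For data already collected:**
- State who knew the arm at each follow-up, and whether notified staff also interviewed.
- Report self-report/biomarker agreement separately by arm.
- Add a sensitivity analysis that compares arms on biomarker outcomes: nail result, DBS at the plan's 700-unit threshold among those on PrEP, and laboratory STI result at 6 and 12 months. Note its limits: the nail window at 3 months predates randomisation, and the plan's own STI calculation has power only for odds ratios of 0.20 to 0.32.

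**Cost:** database permissions, visit order, one recorded item and a modest amount of analysis on data already held. The plan's provision for other staff to cover appointments suggests that no new staff are needed.

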Communication skills. Self-disclosure, social anxiety, assertiveness, and empathy subscales of the Interpersonal Communication Competence Scale (31) assessed aspects of communication skills. Each subscale was assessed by 3 statements (e.g., "I can put myself in others' shoes" and "It's difficult to find the right words to express myself"). Participants evaluated each statement using a 5-point scale Likert-type scale ranging from 0 ("Almost never") to 4 ("Almost always"). Total score reliability was good (Cronbach's $\alpha = .787$).

Quantitative Analysis Plan

The primary hypotheses are that SMM receiving the PARTNER intervention will be more likely to initiate and/or be adherent to PrEP throughout the follow up period. As a result, it is hypothesized they will have a lower probability of TRB. In addition, it is hypothesized that the PARTNER intervention will be associated with lower levels of drug use (number of use instances) compared to the education condition.

Corroboration of self-reported behavior with biomarkers

Self-reported drug use was corroborated by fingernail assays. At baseline and all follow-ups, at least 80% of participants who tested positive for cannabis indicated at least one instance of cannabis use. In addition, at least 60% of those who did not test positive for cannabis on fingernail assays indicated they used cannabis at least once. At baseline, and all follow-ups, at least 55% of those who tested nail positive for cocaine, crack, or amphetamine use reported at least one instance of illicit drug use. In addition, 12% of those who did not test positive for illicit drug use on nail samples self-reported the use of at least one drug.

Self-reported PrEP adherence was corroborated with DBS results. At baseline and all follow-up time points, no fewer than 69% of participants who reported taking their PrEP on 57% of days or more had a DBS test result of 700 units of TFV-DP per DBS punch or greater at all follow-up time points. One participant at baseline and another at the 3month follow-up reported missing more than 57% of their PrEP but produced a DBS result of 700 units of TFV-DP per DBS punch or more.

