Self-reported CAS with casual partners was corroborated by bacterial STI diagnosis. Participants were indicated as having a bacterial STI if they received a positive result for rectal or urethral gonorrhea or chlamydia at baseline, 6, or 12-month follow-up or if they self-reported receiving a diagnosis in the past 3 months at any assessment point. At baseline, 30.5% of those who

reported CAS with a casual partner had a bacterial STI compared to 7.7% of those who did not. Similarly, 44.2% of participants who reported having CAS with a casual partner at either the 3 or 6-month follow-up had a bacterial STI, compared to 23.9% of those who did not. Finally, 39% of those who reported having CAS with a casual partner at the 9 or 12-month follow-up had a bacterial STI compared to 9.5% of those who did not.

Detailed analytic plan

A series of bivariate analyses ($\chi 2$ tests of independence and independent samples t-tests) conducted in SPSS (version 29) evaluated the success of randomization and the presence of differential attrition. The generalized linear model function in SPSS was used to evaluate between-condition differences in baseline frequency of primary outcomes with count distributions (cannabis use days, other illicit drug use days, sexual HIV TRB) and baseline odds of PrEP uptake (a dichotomous variable).

Outcome analyses were conducted using piece-wise latent growth curve (LGC) models following procedures outlined by Chou et al. Growth trajectories over time following the delivery of an intervention may be characterized by a large initial response followed by a more sustained trajectory with a less dramatic slope. Piece-wise LGC models quantify this kind of trajectory using two slopes. Slope 1 quantifies the change from baseline to the immediate post-test (3-month follow-up). Meanwhile, Slope 2 quantifies the trajectory over the post-intervention follow-up period.

Two models were calculated for each outcome. Model 1 included the main effect of treatment on growth factors. Model 2 added the main effects of moderators (communication skills and relationship quality) as well as the interaction terms between these moderators and the main effect of treatment.

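### The primary outcome labelled current PrEP uptake is defined by a lifetime ever-prescribed item, and the plan does not name the PrEP variable in the growth models

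*Combined protocol and SAP*

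**What the plan says.** The abstract's Objectives name PrEP uptake and adherence as one of three primary outcomes. Under MEASURES, Primary outcomes, the plan states: "Current PrEP uptake was assessed using a single survey item". The item it then quotes is "Have you ever been prescribed PrEP (HIV pre-exposure prophylaxis".

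The same paragraph goes on to missed days: "Participants taking PrEP reported days they missed their PrEP on the TLFB interview". It then adds a second variable: "Responses were used to create a dichotomous variable indicating whether or not participants took PrEP on at least 57% of days". The sexual transmission risk behaviour (TRB) outcome in that section also uses PrEP status: "If participants were prescribed PrEP and reported missing 13 doses or fewer, they were assigned a value of 0".

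Elsewhere:

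- **Quantitative Analysis Plan:** the hypothesis is that PARTNER men will be "more likely to initiate and/or be adherent to PrEP throughout the follow up period".
- **Corroboration of self-reported behavior with biomarkers:** the 57% threshold appears under adherence, where dried blood spot (DBS) results are given for "participants who reported taking their PrEP on 57% of days or more".
- **Detailed analytic plan:** the baseline comparison covers "baseline odds of PrEP uptake (a dichotomous variable". The piecewise growth models are described as run for each outcome, without naming the PrEP variable. Slope 1 runs from baseline to 3 months and Slope 2 covers the rest of follow-up.
- **Power analyses:** uptake is powered on 35% of controls taking PrEP, averaged over follow-up, with a detectable odds ratio of 1.90 (about 51% in PARTNER). Adherence is powered separately, in about 100 men on PrEP with 75% of controls adherent.

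**The concern.** The label says current and the item says ever. A lifetime item answered consistently can move from no to yes once and cannot move back. It can show a first prescription, but not whether a man stays on PrEP, stops or restarts.

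That covers only the initiation part of the hypothesis, and only among men never prescribed before baseline. It is also a different quantity from the current-use proportion on which the sample size was justified. With the modelled variable unnamed, a reader cannot tell whether the test for this primary outcome concerns first prescription, current use or use on at least 57% of days.

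**Working it through.** **1. Are men with a prescription before baseline in the trial?** Yes. The eligibility criteria do not exclude PrEP users, the Schedule of Assessments lists a baseline DBS for those on PrEP, and the corroboration section reports baseline DBS results.

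**2. What each scoring records.** Illustrative histories at baseline, 3, 6, 9 and 12 months:

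| History | Ever prescribed | Current use |
|---|---|---|
| Never prescribed, starts by 6 months | 0 0 1 1 1 | 0 0 1 1 1 |
| On PrEP throughout | 1 1 1 1 1 | 1 1 1 1 1 |
| On PrEP at baseline, stops after 3 months | 1 1 1 1 1 | 1 1 0 0 0 |
| Past user, off at baseline, restarts by 3 months | 1 1 1 1 1 | 0 1 1 1 1 |
| Starts by 3 months, stops by 9 months | 0 1 1 1 1 | 0 1 1 0 0 |

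The scorings agree for a first start and for continuous use. They differ in the last three rows, which are stopping and restarting. In rows 3 and 4 the lifetime item shows no change in either slope. In row 5 it shows the start but not the stop. The 57% variable can revert, as current use can.

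**3. The plan's own uptake figure.** Control proportion 0.35, odds ratio 1.90:

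- Control odds = 0.35/0.65 = 0.538; times 1.90 = 1.023; p2 = 1.023/2.023 = 0.506, which matches about 51%.
- Variance factor for the mean of 4 waves at rho 0.75: compound symmetry (1 + 3 × 0.75)/4 = 0.8125; AR(1) 11.594/16 = 0.7246.
- Effective n per arm m = 120/0.8125 = 147.7, or 120/0.7246 = 165.6.
- Power = Φ{[|p2 − p1|√m − 1.96√(2p̄(1 − p̄))]/√(p1(1 − p1) + p2(1 − p2))}, with p̄ = 0.428 and a two-sided 5% test. This gives 0.775 (compound symmetry) or 0.820 (AR(1)).

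The stated odds ratio is therefore reproducible at about 80% power. Its base, 35%, is described as men taking PrEP over follow-up, not men ever prescribed it.

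**4. Which variable is modelled?**

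- For the 57% variable: it is the only PrEP variable that the Primary outcomes section calls dichotomous, and the Detailed analytic plan uses that word for uptake.
- For the survey item: it is the stated measure of uptake, while the corroboration and power sections treat the 57% threshold or adherence as separate from uptake.
- The sentences on the growth models do not settle it.

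**5. How far apart the candidates are, on the plan's inputs.** This assumes that adherent in the power section means the 57% rule.

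- Current use: 0.35 × 120 = 42 control men, 35%.
- 57% variable, men off PrEP scored 0: 0.35 × 0.75 = 0.2625, or 31.5 of 120, about 26%.
- 57% variable, men off PrEP missing: 75%, in about 100 men, or 100/240 = 41.7% of the sample. (The plan's 45% would give 108 of 240 or 86.4 of 192; 100 is used as stated.)
- Lifetime item: no value can be computed, because the share of current non-users with a past prescription is not given.

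**The case against.** The strongest reply is that the paragraph builds a single outcome: a prescription item identifies users, missed days follow, and a dichotomous variable results. The TRB rule has the same structure, and the objective and hypothesis both join uptake with adherence. On that reading the lifetime item is only a gateway and the Slope 2 problem disappears. This reading is possible, so a reader should not infer that the lifetime item was in fact the modelled outcome. It does not close the matter, because uptake is said to rest on a single item and is powered apart from adherence.

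Four further points have weight.

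- A man off PrEP took it on 0% of days, so scoring him 0 on the 57% variable is the natural reading, and it fits the stated retention of all randomised cases. A reader might infer that non-takers drop out of the analysis; the documents do not say that. One explicit line would settle it.
- The power section also describes the PARTNER proportion as initiating PrEP, which a lifetime item captures for men never prescribed before. The 35% control input is still a current-use figure.
- The item's response options and the PrEP uptake questionnaire listed under CASI Measures are not shown, and may separate current from past use. The Primary outcomes section, however, cites only the one item. Its pointer to supplemental material follows the DBS sentence and may cover corroboration only.
- A reader might infer that lapsed users were given zero TRB. The rule requires a report of 13 or fewer missed doses, and nothing says that an absent report was read as none missed. The wording needs tightening, but no miscoding is shown.

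**Conclusion.** The point holds with moderate confidence. Followed as written, the stated rule does not measure current uptake, and the plan does not fix which PrEP variable its growth models test. That is more than missing detail, because the one definition of uptake given conflicts with its label and with the basis of its power calculation.

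The conclusion rests on the item being answered consistently over time and on no unshown response option separating current from past use. If the 57% variable was modelled with men off PrEP scored 0, what remains is a labelling and reporting gap.

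The size of any effect on the result is unknown. An attenuated odds ratio could be produced only by assuming a share of non-users with past prescriptions, and the documents support no such figure. A reader might also infer a bias in favour of PARTNER. Randomisation should balance earlier prescriptions between arms in expectation, so the likely harm is reduced sensitivity to effects on staying on or restarting PrEP.

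**What to change.** 1. State which PrEP variable enters the growth models, and give the survey item's response options.
2. If it is uptake, do not score current uptake from the ever-prescribed item. Score current use at each wave for all randomised men, from timeline follow-back or on-PrEP data or from a named current-use item. Men assessed and not on PrEP score 0; missed assessments are missing.
3. If it is the 57% variable, keep it, say so, and state that men not on PrEP score 0 so that all randomised men are retained.
4. In the TRB zero rule, state that prescribed means taking PrEP in the assessed window.
5. Biomarker corroboration results are already reported in the past tense, so declare any change as post hoc and show the result under the definition now in the plan alongside.

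The cost is wording and recoding, with no new data collection, since the timeline follow-back is scheduled at every assessment. The documents do not say that on-PrEP status is stored as a variable at each wave, so the source used must be named. DBS can serve as a check only where collected: the Schedule of Assessments lists it at every assessment, but the post-COVID kit description places the card at baseline, 6 and 12 months.
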